4.6. Drug Supplies and Labelling

The investigational product will be supplied by UCB Biopharma in blister packs. The investigational medicinal product (IMP) will be labelled and boxed and distributed to site for dispensing by site pharmacies. The patients will be provided with an initial 4 month supply at the Pre surgery (Baseline) visit followed by a three month supply at each scheduled clinic visit.

Details relating to IMP ordering and distribution can be found in the SPRING work instructions for sites.

4.7. Drug Storage and Accountability

Storage

All investigational products must be kept in a secure place under appropriate storage conditions. A description of the appropriate storage and shipment conditions are specified on the investigational labels. Study treatment must be kept out of the reach and sight of children.

Accountability

The investigator or a delegated individual (e.g. pharmacist) must ensure that the study drug is stored and dispensed in accordance with hospital standard operating procedures and applicable regulatory requirements.

The medication provided for this study is for use only as directed in the protocol. Drug distribution and accountability logs will be provided to the site in a pharmacy pack. It is the investigator's responsibility to establish a system for handling the investigational product to ensure that:

- Deliveries of investigational products are correctly received by a responsible person (e.g., pharmacist or suitable pharmacy designee) and are handled and stored correctly and safely
- Investigational products are dispensed only in accordance with the protocol
- Participants return any unused investigational product to the investigator at the end of the trial
- A dispensing record (which will include the identification of the participant to whom the investigational product was dispensed, the date of dispensing, the quantity of investigational product dispensed, and the date and quantity of any unused investigational product returned to the pharmacy) is accurately maintained. Any discrepancies must be accounted for on the appropriate form.

In the case that any study drug is damaged, please contact SCTRU for reconciliation and replacement.

At the termination of the study or at the request of the sponsor, all unused drugs will be accounted for and destroyed locally at the study sites. Certificates of delivery and destruction or return must be signed and copies retained in the Investigator Site File.

Accountability records must be completed and any study drug remaining at the end of the trial must be destroyed according to the sites local standard procedures.

5. PHARMACOVIGILANCE

5.1. Definitions

Adverse Reaction (AR): All noxious and unintended responses related to a study treatment or procedure should be considered adverse drug reactions.

Serious Adverse Event (SAE): Any untoward medical occurrence in a patient that

- a) Results in death
- b) Is life-threatening
- c) Requires hospitalisation or prolongation of existing hospitalisation
- d) Results in persistent or significant disability or incapacity
- e) Consists of a congenital anomaly or birth defect
- f) Is otherwise considered to be medically significant by the investigator (e.g. intensive treatment in an emergency room or at home for allergic bronchospasm or blood dyscrasias).

The term "life-threatening" refers to an event in which the patient was at risk of death at the time of the event; it does not refer to an event which hypothetically might have caused death if it were more severe.

Hospitalisations planned prior to enrolment in the trial or for social reasons should not normally be considered as SAEs unless the hospitalisation has to be prolonged. Treatment in an emergency room of less than 24 hours or on an out-patient basis that does not meet any other serious criteria should not be considered as an SAE.

Suspected Unexpected Serious Adverse Reaction (SUSAR): A suspected unexpected serious adverse reaction (SUSAR) is an adverse reaction that is classified as serious and it is thought to be caused by a study treatment or procedure. Expected events are detailed within the Summary of Product Characteristics (SmPC). The nature, severity or outcome of this adverse reaction must not be consistent with SmPC for the treatment or procedure.

5.2. Emerging safety profile

Levetiracetam is approved for the treatment of patients with newly diagnosed epilepsy. The SPRING trial will use levetiracetam out with this indication to investigate prophylactic use.

This Summary of Product Characteristics (SmPC) lists those events that are to be regarded as expected for regulatory reporting purposes (please refer to the SmPC for any updates). https://www.medicines.org.uk/emc/product/2294/smpc https://www.medicines.org.uk/emc/product/2293/smpc

5.3. Recording and Reporting of Adverse Reactions

All related Adverse Reactions will be recorded in the Case Report Form and graded according to Common Terminology Criteria for Adverse Events (CTCAE) version 5. Any Adverse Reaction considered unrelated will not be recorded.

All adverse reactions that occur after the signing of written informed consent and within 30 days after the final study treatment will be recorded on the appropriate eCRF page. The exception to this would be any event occurring after signing the informed consent and prior to commencing study treatment that is considered unrelated to trial procedures. In addition, any events occurring more than 30 days after final study treatment that are deemed to be related to the study drug should be notified to PHS as detailed in section 5.4.

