3. TRIAL DESIGN

3.1. General Design

This is a two arm, multicentre phase III randomised trial of prophylactic anti-epileptic drug (Levetiracetam) versus no anti-epileptic drug (AED) (comparator) in patients with suspected cerebral glioma.

Randomly assigned - 1:1 basis

This will not be a blinded study and will not have placebo control and as such will be a "real world" study of prophylactic AED vs. no AED. The reasons for the lack of placebo arm include; real world nature of the study, patient involvement feedback on the design with specific reference to value of a placebo arm; over-encapsulation as levetiracetam capsules are large; and cost of the study.

804 patients will be recruited and randomised into one of two arms:

- **Group 1**: Levetiracetam 500mg twice daily for 2 weeks, then increasing to 750mg twice daily thereafter for 1 year. Patients should have a minimum of 2 doses of 500mg prior to surgery. (In those with moderate chronic kidney disease stage 3 estimated Glomerular Filtration Rate (eGFR 30-59 mL/min/1.73 m²) a starting dose of 250mg twice a day for 2 weeks, then increasing to 500mg twice a day thereafter).
- **Group 2**: no AED treatment (standard care)

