- 2) A history and neurological exam (to include documentation of the patient's Karnofsky Performance Status, Semantic Verbal Fluency Test (SVFT)) and an Anterograde Memory test (Recall of a 7 item address after three attempts) will be performed at least every 3 months, +/-2 weeks.
- All patients will be followed for overall survival. Patients will be seen at 3 monthly clinic visits. In addition, all patient reported events will be recorded and safety reporting completed if required (Safety reporting detailed in section 5).

If patients have a seizure they will complete:

- Patient diary
- The Liverpool Impact of Epilepsy Scale (LIES) after first seizure then again one year after randomisation: this is used to assess the impact of epilepsy on a number of different aspects of daily life.
- The Liverpool Seizure Severity Scale (LSSS) will be completed after first seizure and again one year after randomisation.

The EQ5D-5L will be completed after first seizure.

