5.5. Recording and Reporting of Serious Adverse Events

All serious adverse events (not subject to modified safety reporting in section 5.4) that occur after the signing of written informed consent and within 30 days after the final study treatment will be recorded on the SAE report form. Study treatment should be considered any study

activity from informed consent until the final follow up visit or end of final medication (if on IMP arm and in receipt of taper pack). The CTCAE grading will also be captured.

The exception to this would be any event occurring after signing the informed consent and prior to commencing study activity that is considered unrelated to trial procedures. In addition, for patients on IMP arm any events occurring more than 30 days after final study treatment that are deemed to be related to the study drug should be notified to PHS as above.

The SAE case report form must be completed on the Trial eCRF and signed by the Principal Investigator of the centre involved within 24 hours of first becoming aware of the event.

All initial SAE reports should contain the following minimum information:

- Reporter information
- At least one subject identifier (trial number/patient initials)
- Event term
- Assessment of relatedness
- Suspect drug or procedure
- Serious criteria

Sites should email [contact] to notify PHS that an SAE has been reported.

All SAEs for patients on the IMP arm will be forwarded to the CI by PHS for assessment of expectedness against the SmPC. Any SAE that is deemed to be both related and unexpected (i.e. a SUSAR) will be notified to the appropriate Competent Authorities and Research Ethics Committee within 7 days of becoming aware of the event for fatal or life threatening events and 15 days for all other serious events.

Hospitalisations planned prior to enrolment in the trial should not normally be considered as SAEs unless the hospitalisation has to be prolonged. Treatment in an emergency room of less than 24 hours or on an out-patient basis that does not meet any other serious criteria should not be considered as an SAE.

Please refer to SPRING instruction manual for sites for reporting instructions.

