7.3.2 Secondary Efficacy Analysis

The secondary study measures are:

• Time to first seizure

The time to first seizure, within one year of randomisation, will be compared between the study arms using an accelerated failure time model. The acceleration factor and 2sided p-values associated with the comparison of the two study arms from the accelerated failure time model fitted to the timing of a seizure within one year of randomisation will be given.

- Time to first tonic clonic seizure
 The time to first tonic clonic seizure, within one year of randomisation, will be compared
 between the study arms using an accelerated failure time model. The acceleration
 factor and 2-sided p-values associated with the comparison of the two study arms from
 the accelerated failure time model fitted to the timing of a seizure within one year of
 randomisation will be given.
- Patient reported symptoms and adverse events Adverse events will be graded in accordance with CTCAE v5.0. The grade of the tabulated adverse events will be compared between the study arms using a Mann-Whitney U test (exact method).
- Mood, personality, fatigue and memory Mood, personality, fatigue and memory will be assessed through the Liverpool Adverse Events Profile (LAEP) questionnaire. Additionally depressive symptoms will be assessed in detail using the PHQ-9 data. The grade or prevalence of these symptoms will be compared between study arms using a Mann-Whitney U test (exact method).
- Progression Free Survival

Progression will be determined clinically based upon interpretation of MRI scans, clinical state of the patient and steroid dose. Where an MRI is used to determine progression the date of progression will be the date of the scan. If steroid dose is the primary factor in determining progression the date of progression will be the date the dose was started or increased. Where clinical state is used to determine progression the date of progression will be the date of determine progression the date of progression will be the date the dose was started or increased. Where clinical state is used to determine progression the date of progression will be the date of progression the date of progression will be the date of assessment.

Progression free survival will be calculated as the difference between date of progression and date of randomisation.

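### The between-arm test of adverse-event grade draws, for non-serious events, on a record limited to reactions judged related, which an untreated open-label control arm can hardly produce

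*Protocol*

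**What the plan says.** **Recording rule.** Protocol Section 5.3 has related adverse reactions entered in the case report form and graded by CTCAE version 5. It then states: "Any Adverse Reaction considered unrelated will not be recorded".

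**Definition.** Section 5.1 ties a reaction to the trial by definition: "All noxious and unintended responses related to a study treatment or procedure should be considered adverse drug reactions".

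**Design.** Section 3.1: "This will not be a blinded study and will not have placebo control". Group 2 is standard care without an anti-epileptic drug.

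**Analysis.** Section 7.3.2, in the item on patient-reported symptoms and adverse events, says the grade of the "tabulated adverse events will be compared between the study arms" by an exact Mann-Whitney U test. It does not say which records make up the table, or how a patient without an event is scored.

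**Other statements on what is captured.**
- Section 4.2: "all patient reported events will be recorded and safety reporting completed if required".
- Section 6.1 lists adverse events, not adverse reactions, among the data collected.
- Section 5.5 sets no relatedness condition for serious events: "All serious adverse events (not subject to modified safety reporting in section 5.4) that occur after the signing of written informed consent" go on the SAE form with a CTCAE grade. The exceptions are the Section 5.4 list and unrelated events before study activity begins.

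**The concern.** Section 5.3 makes relatedness a condition for an event to exist in the data. In the levetiracetam arm, fatigue or headache can be put down to the drug and recorded. In the control arm the same symptom has no drug to be put down to; only a reaction to a trial procedure could qualify. The investigator makes this judgement knowing the arm.

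The test in Section 7.3.2 treats the two resulting sets of records as comparable. At stake is one listed secondary measure: it could report a toxicity excess on levetiracetam although the drug had added nothing. A later analysis plan cannot repair this, because an event that was never entered cannot be recovered.

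**Working it through.** **1. Arm size.** Section 7.1 uses seizure rates of 20% and 10%, 90% power and two-sided 5%. The pooled-variance formula for two proportions gives 266 per arm, or 532. Attrition: 532 / ((1 − 0.248) × (1 − 0.12)) = 532 / 0.66176 = 803.9, rounded to 804, or 402 per arm. The plan's figures reproduce. They supply only the arm size used below; the protocol states no figure for the adverse-event comparison.

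**2. What can enter the table**

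| Type of event | Levetiracetam | Control |
|---|---|---|
| Non-serious, attributed to drug | recorded (5.3) | cannot occur |
| Non-serious, attributed to a trial procedure | recorded (5.3) | recorded (5.3) |
| Non-serious, judged unrelated | not recorded (5.3) | not recorded (5.3) |
| Serious, outside the 5.4 list, after study activity begins | recorded and graded (5.5) | recorded and graded (5.5) |

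Only the first row differs by arm, and it is the row that holds most non-serious drug reactions.

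**3. Reading A: patients without a recorded event are scored grade 0.** Suppose k patients have a recorded non-serious reaction, all on levetiracetam. This is the most extreme allocation possible, whatever the grades, so the exact two-sided p is

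p = 2 × C(402, k) / C(804, k)

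- k = 5: p = 0.062
- k = 6: p = 0.031

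Six patients, 6 / 402 = 1.5% of the arm, are enough for p < 0.05.

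**4. How often that would happen with no true difference.** The protocol gives no attribution rate, so this step rests on assumptions. Take a true incidence of 15% in both arms and no attribution in the control arm. The exact test then rejects whenever at least 6 treated patients have an event called related. With X binomial (402, 0.15 × share called related):

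| Share called related | Expected recorded patients | P(X ≥ 6) |
|---|---|---|
| 10% | 402 × 0.015 = 6.0 | 0.56 |
| 20% | 402 × 0.030 = 12.1 | 0.98 |
| 50% | 402 × 0.075 = 30.2 | > 0.999 |

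A simulation of the same cases (1,000 runs each, assumed grade mix 60/30/10% for grades 1 to 3) used the normal approximation to the Mann-Whitney test and rejected in 85%, 99.9% and 100% of runs. It is higher in the first rows because the approximation already rejects at 4 versus 0. The exact figures are the relevant ones, since the protocol names the exact method. When all events were recorded regardless of relatedness, the simulated rejection rate was 4.8%, in line with the nominal 5%.

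**5. Reading B: only recorded grades are compared.** The control arm then contributes almost no non-serious grades. The outcome is not a false positive but a test with almost nothing on one side.

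**6. Adding SAEs.** If SAEs are pooled into the table, the control arm is no longer nearly empty. The non-serious records are still added to one arm only, so the comparison remains biased.

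**The case against.** Four stronger readings are tempting, and the protocol does not support them.

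- **That only related events are recorded at all.** Section 5.5 captures and grades SAEs without a relatedness filter. It counts any study activity as study treatment, which brings in the control arm. The near-empty control arm is a statement about non-serious events.
- **That the trial's whole harm comparison is invalid, or that background symptoms are counted in one arm only.** LAEP and PHQ-9 are completed by patients at baseline and every three months (Sections 2.5 and 4.3), and Section 7.3.2 compares them by a separate test. Neither depends on relatedness, although open-label reporting bias remains possible.
- **That the benefit-harm conclusion rests on the CTCAE test.** No section says so. The harm-related objectives in Section 2.3 are mood, personality, fatigue and memory, and quality of life.
- **That the Section 5.4 exemption for memory, mood, personality and fatigue creates the imbalance.** The exemption applies to both arms, and those events are still assessed for relatedness and listed quarterly.

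It can also be argued that Section 4.2 governs, because the item in Section 7.3.2 is framed around patient-reported symptoms. If so, the records would not be filtered. But Section 5.3 is the dedicated recording rule and says the opposite in explicit terms, so this argument shows a contradiction and does not resolve it. Finally, a significant result depends on scoring event-free patients as grade 0, which the protocol does not state. That is correct, and the other reading leaves the test uninformative.

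**Conclusion.** The point holds for non-serious CTCAE-graded events. Under Section 5.3 as written, the between-arm grade test in Section 7.3.2 reflects whether there was a drug to blame, not a difference in harm. This follows from the recording rule, the definition and the open-label untreated control, without any assumed rate.

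The size depends on the scoring. With event-free patients at grade 0, six recorded patients against none is enough for an exact p of about 0.03. The rejection rates of 56% to more than 99.9% rest on an assumed 15% incidence, assumed attribution shares and no attribution in the control arm; they illustrate the mechanism and do not predict this trial. With recorded grades only, there may be almost no control data to test.

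The effect is confined to one secondary comparison. The primary outcome, the sample size and the LAEP and PHQ-9 comparisons are untouched. Separately, Sections 4.2 and 6.1 contradict Section 5.3, and Section 5.3's reference to an unrelated adverse reaction contradicts the Section 5.1 definition, so sites could follow different rules.

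**What to change.** **Preferred.** In Section 7.3.2, remove the between-arm test of Section 5.3 reactions and report those reactions descriptively for the levetiracetam arm. Base between-arm harm comparisons on data captured identically in both arms: SAEs, LAEP and PHQ-9. LAEP and PHQ-9 are already collected and compared, so this is a wording change, and it works whatever has been recorded so far.

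**Alternative.** Record adverse events, or a short prespecified list, at the existing visits in both arms, with relatedness as an attribute and not a filter, and test those. State how patients without an event are scored. The cost is a few eCRF fields; it helps only for visits still to come.

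**In either case.** Reconcile Sections 4.2, 5.3, 6.1 and 7.3.2 so that one recording rule applies at all sites, and define which records form the tabulated adverse events, including whether SAEs are among them.

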5.4. Modified Safety Reporting

The events listed below are expected within the study population and will be exempted from routine SAE reporting, however they will be assessed for relatedness to the study drug and if the event is considered related to study treatment and not expected *i.e.* it is a SUSAR it will be reported in an expedited manner. In addition, a quarterly line listing of these events will be reviewed by the Chief Investigator and sponsor.

- Any Seizure
- Reported changes in memory, mood, personality and fatigue
- Progressive neurological deficit
- Death due to disease progression
- Elective hospitalisation and surgery for treatment of brain cancer or its complications.
- Elective hospitalisation to make treatment or procedures easier.
- Elective hospitalisation for pre-existing conditions that have not been exacerbated by trial treatment.

5.5. Recording and Reporting of Serious Adverse Events

All serious adverse events (not subject to modified safety reporting in section 5.4) that occur after the signing of written informed consent and within 30 days after the final study treatment will be recorded on the SAE report form. Study treatment should be considered any study

activity from informed consent until the final follow up visit or end of final medication (if on IMP arm and in receipt of taper pack). The CTCAE grading will also be captured.

The exception to this would be any event occurring after signing the informed consent and prior to commencing study activity that is considered unrelated to trial procedures. In addition, for patients on IMP arm any events occurring more than 30 days after final study treatment that are deemed to be related to the study drug should be notified to PHS as above.

The SAE case report form must be completed on the Trial eCRF and signed by the Principal Investigator of the centre involved within 24 hours of first becoming aware of the event.

All initial SAE reports should contain the following minimum information:

- Reporter information
- At least one subject identifier (trial number/patient initials)
- Event term
- Assessment of relatedness
- Suspect drug or procedure
- Serious criteria

Sites should email [contact] to notify PHS that an SAE has been reported.

All SAEs for patients on the IMP arm will be forwarded to the CI by PHS for assessment of expectedness against the SmPC. Any SAE that is deemed to be both related and unexpected (i.e. a SUSAR) will be notified to the appropriate Competent Authorities and Research Ethics Committee within 7 days of becoming aware of the event for fatal or life threatening events and 15 days for all other serious events.

Hospitalisations planned prior to enrolment in the trial should not normally be considered as SAEs unless the hospitalisation has to be prolonged. Treatment in an emergency room of less than 24 hours or on an out-patient basis that does not meet any other serious criteria should not be considered as an SAE.

Please refer to SPRING instruction manual for sites for reporting instructions.

